8.1 Protocol Deviations

Major deviations are defined as follows:

- Deviation from main study procedure (audio suggestion) like discontinuation during surgery of more than 10 minutes, wrong treatment in contrast to randomization.
- Violation of inclusion and exclusion criteria.
- Missing informed consent.
- Malfunction of the audio player.
- Unexpected transfer to ICU.

Patients with major deviations will be excluded in the 'per protocol' analysis (see section 7.2).

8.2 Demographic and Baseline Variables

The following variables are considered to be demographic and baseline:

- Medical condition (diseases, medication). Type of surgery.
- Age, sex.
- Pre-operative NRS, HGSHS-5, STAI-S, and Apfel score.
- Duration of surgery.
- Intra-operative analgesic drug dose (opioids and non-opioids).
- Intra-operative analgesic co-medication.
- Intra-operative antiemetic medication.

Demographic and baseline values will be grouped by treatment groups. If applicable, subgroups may be used in accordance with section 7.3. Differences between groups will be investigated as follows: Student's t-test for normally distributed continuous variables, Mann-Whitney U test for not-normally distributed continuous variables, and Pearson's chi-squared test for categorical variables. Tests will be performed two-sided. A p-value of less than 0.05 will be considered to be statistically significant. Demographic and baseline values with p-value will be presented as a table.

9 Efficacy Analyses

For statistical analyses of outcome variables, values will be grouped by treatment groups. If applicable, subgroups may be used in accordance with section 7.3. All continuous, normally distributed variables will be summarized using the following descriptive statistics: n (non-missing sample size), mean, standard deviation (SD). All continuous, not-normally distributed variables will be summarized using the following descriptive statistics: n (non-missing sample size), median, interquartile range (IQR). The point estimates and 95% CI (based on the non-missing sample size) of observed levels and absolute difference of percentage points with 95% CU as well will be reported for categorical measures.

Differences between groups will be investigated as follows: Student's t-test for normally distributed continuous variables, Mann-Whitney U test for not-normally distributed continuous variables, and Pearson's chi-squared test for categorical variables. Tests will be performed two-sided. A p-value of less than 0.05 will be considered to be statistically significant.

Effect sizes for outcome variables will be described by Cohen's d with 95% confidence interval. For dichotomous outcome variables, differences between groups will be expressed as number needed to treat (NNT).

If applicable, all assumptions for regression models will be assessed by viewing plots of the residual values. Analyses of categorical efficacy measures will be performed using logistic regression. Multivariate regression models will be built by a forward stepwise selection process of possible covariates in accordance to literature research.

Results of efficacy analyses will be presented as tables or in text in the final publication(s), including p-values, effect size and NNT.

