4.2 Endpoints

Primary endpoint:

Requirement of pain medication (if patient experiences a pain intensity of NRS \geq 3) during the first 2 and 24 hours after surgery.

For evaluation of primary endpoint post-operative pain levels need to be evaluated by NRS at 0 min (admission to PACU), 15 min, 30 min, 45 min, 60 min, 75 min, 90 min, 105 min, 2 hours and 24 hours.

Secondary endpoints:

Maximum post-operative pain levels (NRS) within 2- and 24-hours post-surgery.

Post-operative nausea and vomiting (PONV) at 2- and 24-hours post-surgery.

Requirement of antiemetic medication in presence of post-operative nausea and vomiting (PONV) during the first 2 and 24 hours after surgery.

Post-operative comfort at 2- and 24-hours post-surgery.

Post-operative anxiety at 2- and 24-hours post-surgery.

Post-operative mental orientation grade after extubation, at admission to PACU and at 2- and 24-hours post-surgery.

Anesthesia wakeup time (time from end of surgery until extubation).

5 Study Methods

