5.4 Study Variables

	Baseline	End of surgery (post extubation)	Post-surgery every 15 min (from admission on PACU until 1 h, 45 mins)	Post-surgery at 2 h after admission on PACU	Post-surgery at 24 h after admission on PACU
History ¹	х				
Age, Sex	х				
NRS ²	х		х	х	х
HGSHS-5 ³	х				
STAI-S ⁴	х			х	х
Apfel ⁵	х				
Duration of surgery		х			x
Intra-operative analgesic drugs ⁶		x			
Intra-operative analgesic co- medication ⁷		х			x
Post-operative analgesic drugs ⁸				х	x
Post-operative analgesic co- medication ⁹				х	x
PONV ¹⁰			х	х	
Wengritzky ¹¹				х	x
Intra-operative antiemetic medication ¹²		х			
Post-operative antiemetic				х	x

	Baseline	End of surgery (post extubation)	Post-surgery every 15 min (from admission on PACU until 1 h, 45 mins)	Post-surgery at 2 h after admission on PACU	Post-surgery at 24 h after admission on PACU
medication ¹³					
Comfort ¹⁴				х	х
Mental Orientation ¹⁵		х	At admission to PACU	х	х
Anesthesia wakeup time ¹⁶		х			
Adverse Events ¹⁷		х	х	х	х

- (1) **History** Medical condition (diseases, medication). Type of surgery.
- (2) **NRS** (Numeric rating scale) Items are measured ranging from 0 to 10 for which 0 = no pain and 10 = worst pain imaginable.¹
- (3) **HGSHS-5** 5-item version of Harvard Group Scale of Hypnotic Susceptibility (ranging from 0 to 5).²
- (4) **STAI-S** State Trait Anxiety Inventory Scale (ranging from 20 to 80).³

¹ Hawker GA, Mian S, Kendzerska T, French M. Measures of adult pain: Visual Analog Scale for Pain (VAS Pain), Numeric Rating Scale for Pain (NRS Pain), McGill Pain Questionnaire (MPQ), Short-Form McGill Pain Questionnaire (SF-MPQ), Chronic Pain Grade Scale (CPGS), Short Form-36 Bodily Pain Scale (SF-36 BPS), and Measure of Intermittent and Constant Osteoarthritis Pain (ICOAP). Arthritis Care Res (Hoboken) 2011;63 Suppl 11(S11):S240-52.

² Bongartz W. German Norms for the Harvard Group Scale of Hypnotic Susceptibility, Form a. Int J Clin Exp Hypn 1985;33(2):131-9.

³ Marteau TM, Bekker H. The development of a six-item short-form of the state scale of the Spielberger State-Trait Anxiety Inventory (STAI). Br J Clin Psychol 1992;31 (Pt 3):301-6.

- (5) Apfel Apfel score of risk for postoperative nausea and vomiting (ranging from 0 to 5).⁴

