7.3 Covariates and Subgroups

If applicable, covariates for analyses (e.g. multivariate regression analysis) will be chosen whether they are expected to have an important influence on endpoints of this study according to literature recherche. Selection of these variables for the final model will be performed by a forward stepwise selection process.

Analyses of subgroups in accordance with covariates which may have an important influence on endpoints may be performed. Covariates will be selected by literature recherche.

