9.2 Secondary Efficacy Analyses

Analyses of secondary endpoints will be performed in accordance with section 9.

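### Post-operative anxiety (STAI-S at 2 h and 24 h) is compared between arms without its own pre-operative value: a valid analysis that gives up precision

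*SAP*

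**What the plan says.** SAP section 4.2 lists as a secondary endpoint "Post-operative anxiety at 2- and 24-hours post-surgery". The instrument is STAI-S, a score from 20 to 80. The schedule in 5.1 and the table in 5.4 place it at baseline, 2 h and 24 h.

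Section 9.2 gives the endpoint no analysis of its own: "Analyses of secondary endpoints will be performed in accordance with section 9". In section 9, group differences are tested by "Student's t-test for normally distributed continuous variables, Mann-Whitney U test for not-normally distributed continuous variables, and Pearson's chi-squared test for categorical variables" (the same sentence also stands in 8.2, for baseline variables). The effect measure is also unadjusted: "Effect sizes for outcome variables will be described by Cohen's d with 95% confidence interval".

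The baseline score appears in 8.2 among the demographic and baseline variables, "Pre-operative NRS, HGSHS-5, STAI-S, and Apfel score", which are tabulated by arm with p-values.

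Adjustment is mentioned only in general terms. Section 7.3 says: "If applicable, covariates for analyses (e.g. multivariate regression analysis) will be chosen whether they are expected to have an important influence on endpoints". It continues: "Selection of these variables for the final model will be performed by a forward stepwise selection process". Section 9 repeats the stepwise approach. The one regression it ties to a type of outcome is logistic, for categorical measures.

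**The concern.** When an outcome has a pre-intervention value on the same scale, that value is the natural covariate for the arm comparison. Here it is collected, but its only committed use is a between-arm test in the baseline table. A raw comparison of the post-operative scores leaves in the error term whatever part of their variation the pre-operative score would explain. The confidence interval for the anxiety effect is then wider than it need be, at both time points.

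The regression provisions do not close this gap. They are conditional, name no covariate for anxiety, and let a data-driven selection rule decide whether baseline STAI-S enters. They also do not say whether an adjusted or an unadjusted result is the one reported for the endpoint.

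**Working it through.** **Inputs from the SAP.** Section 6: 368 patients, 1:1, hence 184 per arm; effect size d = 0.3; two-sided alpha 0.05; about 80% power. These were set for post-operative pain therapy, not for anxiety.

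**Input not in the SAP.** rho, the within-arm correlation between baseline and post-operative STAI-S. It is assumed here at 0.2, 0.3 and 0.5.

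**The plan's own figure.** With d = 0.3, two-sided alpha 0.05 and 80% power:
- normal approximation: 175 per arm, 350 in total;
- noncentral t: 176 per arm, 352 in total;
- two-sided Mann-Whitney U with normally distributed data (relative efficiency 3/pi = 0.955): 184 per arm, 368 in total.

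The last agrees exactly with the stated 368. The SAP does not say which test was entered, so this is a match and not a documented method. A t-test at 184 per arm has 81.9% power.

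**Effect of adjustment on precision.** In a linear regression on arm and baseline score:
- residual variance = (1 − rho²) × unadjusted variance;
- ratio of unadjusted to adjusted standard error = 1/√(1 − rho²).

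These ratios depend on rho alone, not on d or the sample size.

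**Illustrative power.** Standardised effect after adjustment = 0.3/√(1 − rho²). The noncentrality parameter is that effect × √(184/2), and power comes from the noncentral t distribution.

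| rho | Variance reduction (rho²) | Standard error ratio | Standardised effect | Noncentrality | Power |
|---|---|---|---|---|---|
| unadjusted | – | 1 | 0.300 | 2.877 | 81.9% |
| 0.2 | 4% | 1.02 | 0.306 | 2.937 | 83.4% |
| 0.3 | 9% | 1.05 | 0.314 | 3.016 | 85.3% |
| 0.5 | 25% | 1.15 | 0.346 | 3.323 | 91.2% |

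The gains are 1.5, 3.4 and 9.3 percentage points. In equivalent patients, 368/(1 − rho²) gives about 383, 404 and 491 analysed without adjustment.

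**Chance baseline difference.** At 184 per arm the standard error of the baseline difference is √(2/184) = 0.104 SD. A baseline difference of size b shifts the raw estimate by rho × b on average. Even a difference at the edge of significance, 1.96 × 0.104 = 0.204 SD, moves it by only 0.04, 0.06 or 0.10 SD at rho 0.2, 0.3 or 0.5.

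**The case against.** The strongest reply is that nothing here is an error. Under randomisation the raw test is unbiased on average and keeps its 5% type I error, and its standard error already allows for chance baseline differences. This stands: the loss is one of precision.

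Three stronger readings are tempting, and the document does not support them.
- *A chance imbalance in baseline anxiety passes fully into the effect estimate, and drawing lots makes this worse.* It carries over only in proportion to rho. Nor is it particular to simple randomisation: blocks not stratified on anxiety would leave the score about as unbalanced.
- *The anxiety comparison has 81.9% power as planned.* The SAP makes no power claim for anxiety; d = 0.3 and 368 belong to pain therapy. Section 7.1 moreover sets the final analysis after 400 patients. At 200 per arm, before exclusions, unadjusted power at d = 0.3 would be 84.9%, with 86.3% at rho 0.2 and 88.0% at rho 0.3, so the gains are slightly smaller.
- *The same criticism applies equally to maximum NRS.* Pre-operative NRS is collected, but at an assumed rho of 0.2 to 0.3 the gain is only 1.5 to 3.4 points. It adds little and is not part of this point.

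It can also be said that 7.3 foresees covariates with an important influence on endpoints, and that baseline STAI-S is an obvious candidate. That is fair, and adjustment is not excluded. But a candidate in an optional stepwise selection is not a specified term. The unadjusted test remains the only comparison to which the SAP commits for this endpoint.

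Finally, a state-anxiety score before surgery may correlate only weakly with one taken 2 h after admission to PACU. The document offers nothing to settle this, which is why the gain is shown as a range.

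**Conclusion.** The point holds as a matter of efficiency on one secondary endpoint. The planned comparison of STAI-S is valid but leaves an already collected baseline value unused. The unadjusted standard error is about 1.02, 1.05 or 1.15 times the adjusted one if rho is 0.2, 0.3 or 0.5; at the low end the gain is small. The power figures are illustrative only, because they borrow d = 0.3 and 184 per arm from another endpoint. The primary endpoint and the sample size are not affected. A reader might infer that the planned anxiety result would be biased or its type I error inflated. The document does not support that: allocation is randomised, and averaged over possible allocations the test performs as stated. The change is still worth making, because it costs almost nothing and fixes in advance which result is reported.

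**What to change.** In section 9.2, state that STAI-S at 2 h and STAI-S at 24 h are each analysed by linear regression with treatment arm and baseline STAI-S as always-included terms, outside any stepwise selection. The reported result is the adjusted mean difference in STAI-S points with its 95% CI and p-value. If residuals are clearly non-normal, use robust or bootstrap standard errors. Keep the t-test or Mann-Whitney U as a supporting analysis.

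Add that a missing baseline STAI-S is replaced by the overall mean of both arms together. Otherwise section 7.4, which excludes missing data from each analysis, would drop a patient whose post-operative score is available.

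The cost is a sentence or two of SAP wording and a standard regression. No new data are needed.

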- (6) Intraop. analgesic drugs Sum of sufentanil dose, sum of fentanyl dose, sum of piritramide dose, sum of metamizole dose, sum of paracetamol dose, sum of COX2-inhibitor (cyclooxygenase 2) dose. Cumulative dosage of non-opioids as percentage of maximum daily dose (maximum daily doses for conversion: metamizole=4000mg, paracetamol=4000mg, ibuprofen=2400mg, diclofenac=150mg).
- (7) **Intraop. analgesic Co-medication** Sum of clonidine dose.
- (8) Postop. analgesic drugs - Sum of opioid dose represented as morphine piritramide=0.7, tilidine=0.2, equivalents (factors for conversion: tramadol=0.1, oxycodone=2.0). Sum of metamizole dose, sum of paracetamol dose, sum of ibuprofen dose, sum of diclofenac dose, sum of COX2-inhibitor (cyclooxygenase 2) dose. Cumulative dosage of non-opioids as percentage of maximum daily dose (maximum daily doses for conversion: metamizole=4000mg, paracetamol=4000mg, ibuprofen=2400mg, diclofenac=150mg).
- (9) **Postop. analgesic Co-medication** Sum of clonidine dose.
- (10) **PONV** (post-operative nausea and vomiting) Items are 'true' or 'false', depending on patient reporting nausea or vomiting within the specified time interval.
- (11) Wengritzky PONV impact scale score (ranging from 0–6), a score of ≥ 5 defines clinically important PONV.⁵
- (12) Intraop. antiemetic medication Sum of granisetron dose, sum of ondansetron dose, sum of dexamethasone dose, sum of droperidol dose.

⁴ Apfel CC, Heidrich FM, Jukar-Rao S, et al. Evidence-based analysis of risk factors for postoperative nausea and vomiting †. Br J Anaesth 2012;109(5):742-53.

⁵ Myles PS, Wengritzky R. Simplified postoperative nausea and vomiting impact scale for audit and post-discharge review. Br J Anaesth. 2012 Mar;108(3):423-9.

- (13) Postop. antiemetic medication Antiemetics Milligram Equivalents
 (ondansetron = 4, dexamethasone = 4, droperidol = 1.25, metoclopramide = 20, dimenhydrinate = 50).⁶
- (14) **Comfort** Scale items are measured ranging from 0 to 10 for which 0 = no comfort and 10 = highest comfort.
- (15) Orientation grade Items are 'full', 'mostly', 'partly' and 'not'. Patients will be asked for their name, location and day of week (3 correct answers = full, 2 correct answers = mostly, 1 correct answer = partly, no correct answer = not).
- (16) Anesthesia wakeup time Time from end of surgery until extubation.
- (17) Adverse events all adverse events during study visits will be documented.

6 Sample Size

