On basis of a 1:1 randomization ratio, we calculated that a planned sample of 368 patients would provide the trial with approximately 80% power to detect a difference in postoperative pain therapy on the basis of an effect size of 0.3 at a two-sided alpha level of 0.05. With 5 participating study centers, approximately 70-80 patients need to be included per center.

The sample size calculation is based on a previously published meta-analysis by Rosendahl et al.⁷ Sample size calculation for a power of 80% was done using G*Power software (University Dusseldorf, Dusseldorf, Germany, http://www.psychologie.hhu.de/arbeitsgruppen/allgemeine-psychologie-undarbeitspsychologie/gpower.html).

⁶ Apfel CC, Korttila K, Abdalla M, et al. A Factorial Trial of Six Interventions for the Prevention of Postoperative Nausea and Vomiting. N Engl J Med 2004; 350(24): 2441-51.

⁷ Rosendahl J, Koranyi S, Jacob D, Zech N, Hansen E. Efficacy of therapeutic suggestions under general anesthesia: A systematic review and meta-analysis of randomized controlled trials. BMC Anesthesiol 2016;16(1).

 Caseley-Rondi et al. 1994; d = 0.459
 Korunka et al. 1992; d = 0.405
 Rosenberg et al. 1992; d = 0.384
 Williams et al. 1994; d = 0.323
 Mastropietro et al. 1998; d = 0.315
 Furlong-Read et al. 1993, d = 0.256
 Nilsson et al. 1993; d = 0.244

7 General Considerations

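### The orientation grade has four ordered levels, but section 9's default test for categorical variables ignores the order; a minor, cheaply corrected loss of power on one secondary endpoint

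*SAP*

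**What the plan says.** SAP section 4.2 lists among the secondary endpoints: "Post-operative mental orientation grade after extubation, at admission to PACU and at 2- and 24-hours post-surgery". Section 5.4, item 15, defines the grade from three questions: "3 correct answers = full, 2 correct answers = mostly, 1 correct answer = partly, no correct answer = not".

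Section 9.2 gives no test specific to this endpoint: "Analyses of secondary endpoints will be performed in accordance with section 9". Section 9 then offers three between-group tests: Student's t-test for normal continuous variables, "Mann-Whitney U test for not-normally distributed continuous variables", and "Pearson's chi-squared test for categorical variables". It adds: "Analyses of categorical efficacy measures will be performed using logistic regression". The form of that regression (binary, ordinal or multinomial) is not stated.

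For effect size, section 9 says "Effect sizes for outcome variables will be described by Cohen's d with 95% confidence interval", with NNT for dichotomous outcomes. No measure is named for an ordered category. The SAP names no ordinal or trend test and no rule for sparse tables.

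**The concern.** The grade is a count of correct answers, so its order is part of its definition. Pearson's chi-squared on a 2×4 table spends three degrees of freedom looking for any difference between the arms and gives the same answer if the four columns are shuffled. If the audio suggestions help, the natural expectation is a shift towards better orientation. A test that uses the order puts its power on that pattern and needs only one degree of freedom. A real shift would therefore be missed more often than the data require. The open form of the logistic regression also leaves a choice that could be made after the results are seen.

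**Working it through.** **Inputs from the SAP.** Four ordered levels (section 5.4, item 15). 1:1 allocation, two-sided alpha 0.05, effect size 0.3 and 368 patients, so 184 per arm (section 6). The SAP gives no expected distribution of the grade and no power for it.

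**The plan's own figure.** Section 6 says "a planned sample of 368 patients would provide the trial with approximately 80% power"; this concerns postoperative pain therapy, not orientation. A t-test with d = 0.3 needs 176 per arm (352). For the Mann-Whitney test with normal data (efficiency 3/π), the effective size is 184 × 3/π = 175.7 per arm and the noncentrality is 0.3 × √(175.7/2) = 2.81. Power is 80.1%, so 368 is reproduced exactly. I therefore use 184 per arm.

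**Check that needs no assumed distribution.** Suppose a 1-df test captures the whole shift and has 80% power. Its noncentrality is (1.960 + 0.842)² = 7.85. The same noncentrality on 3 df gives 64% power. Reaching 80% on 3 df needs 10.90, and 10.90/7.85 = 1.39, so about 39% more patients.

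**Simulation.** 40,000 trials per scenario, 184 per arm. The treated arm is the control arm shifted by a common odds ratio (OR). An OR of 1.72 corresponds to d = 0.3 on the logistic scale: exp(0.3 × π/√3) = exp(0.544) = 1.72. Chi-squared is computed without continuity correction, with empty columns dropped. The Mann-Whitney test uses midranks and variance n₁n₂/12 × [(N+1) − Σ(c³−c)/(N(N−1))], where c is the total count at each level. The control distributions are assumptions.

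| Time; control not/partly/mostly/full (%) | Chi-squared power, OR 1.72 | Mann-Whitney power, OR 1.72 | Loss (points) |
|---|---|---|---|
| After extubation; 15/20/25/40 | 64.3% | 79.9% | 15.6 |
| PACU admission; 5/15/30/50 | 59.3% | 76.3% | 17.0 |
| 2 h; 1/4/15/80 | 31.5% | 47.3% | 15.8 |
| 24 h; 0.25/0.75/3/96 | 6.8% | 13.9% | 7.1 |
| 24 h; 0.1/0.4/1.5/98 | 4.1% | 8.3% | 4.2 |

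Over odds ratios 1.5 to 2.0, the loss at the first three times runs from 8.7 points (85.9% against 94.6%, after extubation, OR 2.0) to 18.0 points (48.1% against 66.1%, 2 h, OR 2.0).

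**Type I error (OR 1).** Chi-squared: 5.0%, 4.9% and 4.2% at the first three times, and 2.5% and 2.4% in the two 24 h scenarios. Mann-Whitney: 5.0%, 5.1%, 4.8%, 4.8% and 4.4%. The power gain is not bought with false positives.

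**Sparse cells in the 24 h scenarios.** With no effect, expected counts per arm are 0.5/1.4/5.5 for not/partly/mostly at 96% full, and 0.2/0.7/2.8 at 98% full.

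**A case against the rank test.** Control 5/10/25/60, treated 1/5/34/60: patients move up from the two lowest levels, but the share fully oriented does not change. Chi-squared has about 80% power and Mann-Whitney about 11%.

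**The case against.** **Chi-squared is only inferred.** The SAP never expressly calls the grade categorical, and a 0–3 count could be ranked like its other bounded scores. This is possible, but the levels are given as words without a numeric score, and section 9 limits Mann-Whitney to continuous variables. The categorical reading is the natural one, and the other reading would still need a clarifying sentence.

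**Logistic regression is also planned.** This is true. A binary version (full against not full) would lose little. At OR 1.72 a chi-squared test of that split has 74.5%, 73.3% and 47.3% power at the first three times, against 79.9%, 76.3% and 47.3% for the rank test. But the form is not stated, a multinomial model would again ignore order, and chi-squared remains the named between-group test. The objection narrows the point without removing it.

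**The simulations favour the rank test.** They assume a consistent shift, so part of its advantage is built in. The last example shows the reverse. This stands: the change has a downside, although a shift towards better orientation is the more plausible effect.

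**Pearson's test is valid where cells are well filled, and little depends on it.** This also stands. Orientation is one of seven listed secondary endpoints and was not the basis of the sample size.

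**A stronger reading to avoid.** A reader might infer that the cells are near-empty by 24 h and that this causes the power loss. The SAP gives no frequencies, so the sparsity is only plausible. The large loss arises at the earlier, better-filled times.

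**Conclusion.** The point holds as a minor one. The grade is ordered by its definition, and the default rule of section 9 gives it an unordered 3-df test. Under the assumed distributions and a common odds ratio of about 1.7, the cost is roughly 15 to 17 points of power after extubation, at PACU admission and at 2 h (about 9 to 18 points over odds ratios 1.5 to 2.0). These figures depend on the assumed distributions and on a consistent shift.

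If 96% to 98% of patients are fully oriented at 24 h, chi-squared rejects about 2.5% of the time under no effect. That is conservative, so it gives no ground for fearing false positives. The ordered test would then have only 8% to 14% power at OR 1.72, so changing the test recovers little at 24 h. A reader might also infer that the binary outcomes need Fisher's exact test; nothing here shows a defect in them. The primary analysis is unaffected.

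**What to change.** In section 9:

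- Class the orientation grade as ordinal.
- Replace chi-squared for it, at each of its four times, with a tie-corrected Mann-Whitney test. Use a permutation p-value for that test if any expected count is below 5.
- State that the logistic regression is proportional-odds for this endpoint, and report the common odds ratio with 95% CI as its effect measure.
- Add a check of the proportional-odds assumption.

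This takes two or three sentences and no extra data. The cost is lower power if the effect is not a consistent shift across the levels, and one more model assumption to check. The change should be fixed before the data are unblinded.

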7.1 Timing of Analyses

The final analysis will be performed after participation of 400 patients in this study.

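### Optional subgroup analyses are sent to treatment-arm tests at p<0.05, and no treatment-by-subgroup interaction test is specified

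*SAP*

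**What the plan says.** SAP section 7.3 (Covariates and Subgroups) makes subgroup analyses optional and leaves the choice of factors to a literature search: "Analyses of subgroups in accordance with covariates which may have an important influence on endpoints may be performed". It names no subgroup factor and gives no number of subgroups.

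Section 9 (Efficacy Analyses) admits these subgroups to the outcome analysis: "For statistical analyses of outcome variables, values will be grouped by treatment groups. If applicable, subgroups may be used in accordance with section 7.3". It then sets the tests: "Differences between groups will be investigated as follows: Student's t-test for normally distributed continuous variables, Mann-Whitney U test for not-normally distributed continuous variables", with Pearson's chi-squared test for categorical variables. All tests are two-sided, and p below 0.05 counts as significant. Section 9 also asks for Cohen's d with a 95% confidence interval, percentage-point differences with intervals for categorical measures, and the NNT for dichotomous outcomes.

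The regression paragraph of section 9 adds logistic regression for categorical measures and multivariable models: "Multivariate regression models will be built by a forward stepwise selection process of possible covariates in accordance to literature research". It mentions no product of treatment and covariate. The SAP contains no interaction or heterogeneity test.

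**The concern.** A treatment-arm test run inside a subgroup has the null hypothesis of no effect in that subgroup. The usual reason for a subgroup analysis is to ask whether the effect differs between subgroups, and the null for that is an equal effect in all of them. No test in the SAP has that null.

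The trial is sized for about 80% power in the whole sample, so a half-sample has only about 50%. Even if the audio suggestions worked equally well in everyone, one significant and one non-significant subgroup would be a common chance result. The trial enrols two surgical populations and measures hypnotic susceptibility. These are plausible factors, although the SAP selects neither. What is at stake is a published statement that the suggestions help only one kind of patient, when the data show no such difference.

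**Working it through.** **Inputs.** From section 6 (Sample Size): "a planned sample of 368 patients would provide the trial with approximately 80% power", "on the basis of an effect size of 0.3 at a two-sided alpha level of 0.05", with 1:1 allocation, so 184 per arm. From section 7.1: "The final analysis will be performed after participation of 400 patients in this study", so 200 per arm. Assumed, because the SAP is silent: two subgroups, the split sizes, a continuous and roughly normal outcome, and 1:1 allocation within each subgroup.

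**The plan's own figure.** A noncentral-t calculation for a t-test at d=0.3 and 80% power needs 176 per arm, or 352 in total. For a Mann-Whitney test, n is multiplied by the asymptotic relative efficiency 3/π = 0.955. Then 184 per arm acts like 184 × 0.955 = 175.7, power is 80.1%, and the total is 368. The planned figure is reproduced on the Mann-Whitney basis. A t-test with 368 patients has 81.9% power.

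**Power within a subgroup.** Two equal halves have 184/2 = 92 per arm each. The standard error of a standardised difference is √(2/92) = 0.147, so d/SE = 0.3/0.147 = 2.03, just above the critical value of 1.96. Noncentral-t power is 52.6% for the t-test and 50.7% for Mann-Whitney.

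**Chance of a discordant pair.** The subgroups are independent, so P(exactly one significant) = p1(1−p2) + p2(1−p1).

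- t-test: 2 × 0.526 × 0.474 = 0.499. Both are significant in 27.6% of trials and neither in 22.5%.
- Mann-Whitney: 2 × 0.507 × 0.493 = 0.500. Both 25.7%, neither 24.3%.
- 70:30 split, t-test: 0.669 × 0.654 + 0.346 × 0.331 = 0.552.
- 400 patients, equal halves: 49.3% (t-test) or 49.7% (Mann-Whitney).

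**Sensitivity to the true effect** (368 patients, equal halves):

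| True d in both halves | Exactly one significant |
|---|---|
| 0 | 9.5% |
| 0.1 | 18% (Mann-Whitney) |
| 0.2 | 40% (t-test), 39% (Mann-Whitney) |
| 0.3 | 50% |
| 0.4 | 35% (t-test), 37% (Mann-Whitney) |
| 0.459 | 25% (Mann-Whitney) |

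The last value of d is the largest study effect listed in section 6.

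**Interaction test under the same uniform effect.** The statistic is the difference between the two subgroup estimates divided by its standard error. In 1,000,000 simulated pairs of estimates at d=0.3, it exceeded 1.96 in absolute value in 5.0% of cases, for both the 50:50 and the 70:30 split.

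**Power of the interaction test when effects do differ.** For equal halves the standard error of the difference is √(4/92) = 0.209. For true effects of 0.45 and 0.15, 0.30/0.209 = 1.44 and power is about 30%. For 0.6 and 0, 0.60/0.209 = 2.88 and power is about 82%.

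**The case against.** The strongest reply is that the SAP does not contain the faulty inference. Subgroup analyses are optional, and no sentence says that a significant result in one subgroup and a non-significant one in another will be taken as a subgroup-specific effect. A reader might infer such a rule, and might conclude that about half of trials would end in a false claim. The documents do not support either step: the 50% is the frequency of a pattern, and the SAP sets no claim rule on it.

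Three further points stand.

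- The sentence admitting subgroups also appears in section 8.2 for baseline variables, where effect modification is not at issue. It may be only a general permission to break tables down. Testing within subgroups is the natural reading of section 9, but the section does not spell it out.
- Significance tests are not all that section 9 offers. Cohen's d with its interval, percentage-point differences with intervals, and regression are there too. Overlapping intervals would warn a careful reader, although they do not replace a test of heterogeneity.
- Discordance is the most frequent pattern only near the planning effect. At d=0.2, neither subgroup is significant in 53% of trials; at d=0.4, both are in 59%. At d=0.3 with equal halves, a discordant result favouring one particular subgroup has probability of only about 25%.

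The gap remains all the same. Section 9 is where the SAP sends subgroup analyses, and nothing there tests whether effects differ or limits how discordant p-values may be read.

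**Conclusion.** The point holds as a gap in how the optional subgroup analyses are specified. Run as written, they would give arm comparisons within subgroups and no test of a difference between them. With a uniform true effect of d=0.3 and two about equal subgroups of 368 patients, exactly one subgroup is significant in about 50% of trials, roughly ten times the 5% false-signal rate of an interaction test.

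That figure depends on the assumed split, a roughly normal outcome and a true effect near 0.3. It falls to about 35-40% at d=0.4 or 0.2 and to 9.5% with no effect. At d=0.3 it rises with unequal splits, to 55% at 70:30. The issue concerns the interpretation of subgroup results and does not touch the primary comparison.

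**What to change.** Add to sections 7.3 and 9 that any claim of a differing effect between subgroups rests on a test of treatment-by-subgroup interaction. This means one product term per factor in the linear, ordinal or logistic model that suits the outcome. Report each subgroup's effect estimate with its 95% CI and label the results exploratory. Leaving out within-subgroup p-values, or entering hypnotic susceptibility as a continuous modifier, is a matter of preference and not needed to close the gap.

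The cost is a few sentences and one model term per factor, on data already collected. The real downside is low power for modest interactions (about 30% for d=0.45 against 0.15 in equal halves), so fewer subgroup claims can be made.
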